6.3 Safety procedures

6.3.1 Enrolment and screening

At enrolment, each potential patient will provide informed consent prior to starting any study specific procedures (see Appendix D of this Clinical Study Protocol for Ethics and Regulatory Requirements).

Each potential patient is assigned a unique enrolment number by a nominated person at AstraZeneca. Recruitment into the study will be conducted in a controlled manner. No patient will be enrolled without prior authorisation from AstraZeneca to ensure adherence with the rolling 6 recruitment design and subsequent allocation to expansion cohorts. If a patient withdraws from the study, then the enrolment code cannot be reused.

Demographic data and other characteristics will be recorded and will include date of birth or age, gender, race and/or ethnicity according to local regulations, smoking history.

A standard medical, medication and surgical history will be obtained with review of the selection criteria with the patient.

Each patient will undergo screening (see Study Plan Table 2, Table 3 and Table 4) during the 28 days prior to admission to confirm eligibility (see Sections 4.1. and 4.2). Tumour assessments and other clinical data obtained as standard of care prior to consent may be used for the study provided the assessments fall within the protocol specified period prior to the first dose of study treatment. Tumour receptor/mutation status will be recorded including EGFRm, T790M and cMET etc.

Prior to discharge from each in-patient and clinic visit, the Investigator or their deputy will be responsible for reviewing all available data including vital signs and ECG tracings.

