6.4.1 Definition of adverse events

An adverse event is the development of an undesirable medical condition or the deterioration of a pre-existing medical condition following or during exposure to a pharmaceutical product, whether or not considered causally related to the product. An undesirable medical condition can be symptoms (eg, nausea, chest pain), signs (eg, tachycardia, enlarged liver) or the abnormal results of an investigation (eg, laboratory findings, electrocardiogram). In clinical studies, an AE can include an undesirable medical condition occurring at any time, including run-in or washout periods, even if no study treatment has been administered.

For patients in Japan: For cases where it could be suspected that a tissue-derived medicine has been contaminated by a pathogen, information about any of the above conditions (including infection) should be collected.

Any deterioration of the disease under study and associated symptoms or findings should not be regarded as an adverse event as far as the deterioration can be anticipated (see Section 6.4.3).

The term adverse event is used generally to include any AE whether serious or non-serious.

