6.4.3 Recording of adverse events

Time period for collection of adverse events

AEs will be collected throughout the study, from informed consent until the end of the followup period. The follow-up period is defined as 28 ± 7 days after study treatment is discontinued. SAEs occurring in the follow-up period should be reported to AstraZeneca in the usual manner (see Section 6.4.4).

Following discontinuation of AZD9291, SAEs considered related to study procedures should continue to be collected while patients are followed up for disease progression.

After the final database lock, there may be some patients remaining on study treatment. For these patients who are continuing to receive AZD9291 AZ will collect information (during the treatment period and for 28 +/- 7 days after last dose) on SAEs, deaths (including those due to disease progression), discontinuation due to AEs/SAEs and drug accountability only.

Follow-up of unresolved adverse events

Any AEs that are unresolved at the patient's last visit in the study are followed up by the investigator for as long as medically indicated, but without further recording in the CRF. AstraZeneca retains the right to request additional information for any patient with ongoing AE(s) at the end of the study, if judged necessary.

If an investigator learns of any SAEs, including death, at any time after a patient has completed the study and he/she considers there is a reasonable possibility that the event is related to AZD9291, the investigator should notify AstraZeneca.

Variables

The following variables will be collected for each AE:

- AE diagnosis/description
- The date when the AE started and stopped
- Maximum CTCAE grade
- Whether the AE is serious or not
- Investigator causality rating against the investigational product (yes or no)
- Action taken with regard to investigational product

• Outcome

For SAEs other variables will be collected including treatment given for the event.

It is important to distinguish between serious and severe AEs. Severity is a measure of intensity whereas seriousness is defined by the criteria in Section 6.4.2. An AE of severe intensity need not necessarily be considered serious. For example, nausea that persists for several hours may be considered severe nausea, but not a SAE. On the other hand, a stroke that results in only a limited degree of disability may be considered a mild stroke but would be a SAE.

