Data from all cycles of initial treatment will be combined in the presentation of safety data. AEs will be listed individually by patient and dose group. For patients who have a dose modification, all AEs (due to drug or otherwise) will be assigned to the initial dose group. The number of patients experiencing each AE will be summarised by the Medical Dictionary for Regulatory Activities (MedDRA) system organ class, MedDRA preferred term and CTCAE grade. The number and percentage of patients with adverse events in different categories (eg, causally related, CTCAE grade \geq 3 etc) will be summarised by dose group, and events in each category will be further summarised by MedDRA system organ class and preferred term, by dose group. SAEs will be summarised separately if a sufficient number occur.

Any AE occurring before the first dose of investigational product (ie, before study Day 1) will be included in the data listings but will not be included in the summary tables of adverse events.

Any AE occurring within the defined 28 day follow-up period after discontinuation of investigational product will be included in the AE summaries. Any adverse events in this period that occur after a patient has received further therapy for cancer (following discontinuation of investigational product) will be flagged in the data listings. AEs occurring after the 28 day follow-up period after discontinuation of investigational product will be listed separately, but not included in the summaries.

Haematology, clinical chemistry, vital signs, ECG data, ophthalmic examination data, demographic data and concomitant medications will be listed individually by patient and suitably summarised. For all laboratory variables, which are included in the current version of CTCAE, the CTCAE grade will be calculated. Summary statistics of mean, median, standard deviation, minimum, maximum and number of observations will be used.

Details of any deaths will be listed for all patients.

Any qualitative assessments will be summarised for all patients using the number of patients with results of negative, trace or positive.

Graphical presentations of safety data will be presented as is deemed appropriate. This may include, but is not restricted to, presentation of parameters against time, concentration or shift plots. Appropriate scatter plots will also be considered to investigate trends in parameters compared to baseline.

Pharmacokinetics

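### An AE that starts between consent and first dose and then worsens on AZD9291 can be left out of the AE summary tables, depending on how the site records it

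*Protocol*

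**What the plan says.** Three parts of the protocol bear on this.

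- **The tabulation rule (Section 7.9, Safety).** Its scope is set by date: "Any AE occurring before the first dose of investigational product (ie, before study Day 1) will be included in the data listings". Such events "will be included in the data listings but will not be included in the summary tables of adverse events". No clause deals with an event that begins before first dose and increases in grade afterwards. The same part of 7.9 sets out the tables concerned: AEs by system organ class, preferred term and CTCAE grade, and by category, including causally related events and events of grade 3 or above.
- **What is collected (Section 6.4.3).** "AEs will be collected throughout the study, from informed consent until the end of the followup period". The variables for each AE include "The date when the AE started and stopped" and "Maximum CTCAE grade", together with seriousness, causality, action taken with the investigational product and outcome. A dated change of grade is not among them.
- **What counts as an AE (Section 6.4.1).** The definition covers "the deterioration of a pre-existing medical condition following or during exposure to a pharmaceutical product". It also allows an AE to be "an undesirable medical condition occurring at any time, including run-in or washout periods, even if no study treatment has been administered".

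Section 6.3.1 places screening "during the 28 days prior to admission to confirm eligibility", so an AE can start up to about four weeks before dosing.

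**The concern.** Excluding pre-dose events from AE tables is ordinary practice. It normally comes with a provision that an event which worsens on treatment is counted from the worsening. Here the exclusion is written into the protocol without that provision, and the listed AE variables would not let an analyst add it later within a single record.

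At stake is whether the AE tables count the same thing at every site. The study is multicentre. Two sites could see the same course of events, one opening a second record and the other updating the maximum grade on the first, and only the first site's event would be tabulated. Any resulting error goes one way, because worsening on drug can be lost but cannot be over-counted. Section 7.1 lists safety and tolerability as primary for the escalation and expansion cohorts, and Section 1.1 includes them in the study's primary objective.

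The setting makes such events plausible. Section 4.2 requires about 8 days or five half-lives off an EGFR TKI (whichever is longer) and 14 days off chemotherapy. Both can fall inside the 28-day screening window, so symptoms may start after consent and continue into treatment. Section 3.2 names rash and diarrhoea as toxicities seen with first-generation EGFR TKIs.

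**Working it through.** The plan gives no figure to reproduce and no formula applies. The check is to follow one event through the sections under each way of recording it.

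**Illustrative event.** Grade 1 diarrhoea starts on Day -5, after consent. It continues past first dose and reaches grade 3 on Day 12 of AZD9291.

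**Step 1: is the Day -5 event an AE?** Yes. Section 6.4.1 allows AEs before any study treatment, and Section 6.4.3 collects them from consent.

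**Step 2: how is the Day 12 worsening recorded?** Section 6.4.3 does not say. There are two possibilities.

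| | One record, updated | New record at worsening |
|---|---|---|
| Start date | Day -5 | Day 12 |
| Maximum grade | 3 | 3 |
| Before first dose by start date? | Yes | No |
| In the 7.9 summary tables? | No | Yes |
| In the listings? | Yes | Yes |

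**Step 3: do the documents choose between the columns?**

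- Section 6.4.1 supports the right-hand column, because deterioration during exposure is itself within the AE definition. That is a definition, however, not a recording instruction.
- Section 6.4.3 has an aggravation rule measured against baseline for physical-examination findings. Its paragraph on signs and symptoms, which would govern diarrhoea, has no equivalent.
- The single maximum-grade field fits the left-hand column: a site that holds an open AE and sees it worsen has a field to update.

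**Step 4: could the analysis recover the event under the left-hand column?** Not from the listed variables. The record shows a pre-dose start, a maximum grade of 3 and perhaps an action taken with study drug. It does not show when grade 3 was reached, or the grade at first dose. An analysis plan can add a worsening rule, but it cannot apply one to grade changes that were never dated.

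**Step 5: size.** The documents give no rate of AEs starting between consent and first dose, and no rate of later worsening. The number of events lost lies between none (every worsening entered as a new AE) and all such worsenings (every one kept in its pre-dose record).

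**The case against.** The best reply is that Section 7.9 excludes AEs occurring before first dose, and that under Section 6.4.1 a deterioration on AZD9291 is an AE occurring after it. On that reading nothing is lost. The recording detail could sit in the CRF instructions that Section 6.2 mentions, and a treatment-emergent derivation is commonly left to the analysis plan; neither document is shown.

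Much of this stands. A reader might infer that 6.4.1 and 7.9 contradict each other. They do not: the two are compatible if worsening is recorded as a new event. What remains is that the protocol never tells sites to do so for symptoms, while it does fix both the date-based exclusion and a data set without dated grades. That goes beyond detail deferred to an analysis plan.

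Other stronger inferences also fail:

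- **That these events vanish from the safety assessment.** They remain in the listings. DLTs are assessed separately (Section 5.1.3), and the category for other toxicity is judged against baseline. Laboratory, vital-sign and ECG data have their own summaries. These safeguards are partial: DLT assessment covers the escalation cohorts only, not the approximately 162 expansion and 175 extension patients, and laboratory, vital-sign and ECG summaries do not capture symptoms.
- **That all residual toxicity from prior therapy is affected.** Toxicity that pre-dates consent is a pre-existing condition, not an AE already on record, so its worsening on drug would naturally be entered as a new AE. The gap concerns events that start between consent and first dose.
- **That the zero-event statement in Section 7.2.4 becomes wrong.** That statement is conditional on observing no events among 175 patients and does not say which records feed the count.

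**Conclusion.** The point holds as a gap in recording and counting. Under the protocol as written, an AE with onset between consent and first dose that worsens on AZD9291 can be left out of the AE tables by grade, of grade 3 or above, and of causally related events. Whether it is left out depends on the site's recording habit.

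This rests on two assumptions: that the exclusion is applied by AE start date, and that no instruction outside the protocol tells sites to open a new record on worsening. If either is false, the loss may be nil. The documents do not allow the number to be estimated, and it could be zero. They do not support saying that worsening is always dropped or that it is missing from the primary safety endpoint. The case for acting is that any error runs only towards under-reporting, the change is small, and undated grade changes may be hard to recover later.

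**What to change.** Make two changes.

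1. **Section 7.9:** exclude AEs with onset before first dose from the summary tables unless they increase in CTCAE grade on or after first dose; in that case, count them at the on-treatment grade.
2. **Section 6.4.3:** instruct sites to record such a grade increase as a new AE entry dated at the worsening, leaving the pre-dose entry in the listings.

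For patients already treated, the records to query are those with a start date before first dose that were still ongoing at first dose. Their number is an upper limit on the single-record AEs affected.

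The cost is one sentence, one CRF instruction and a limited data query. Reported AE counts may rise slightly. Because the tables count patients, a patient with both a pre-dose entry and a worsening entry would still be counted once for that event.

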4.2 Exclusion criteria

Patients must not enter the study if any of the following exclusion criteria are fulfilled

- 1. Treatment with any of the following:
 - Treatment with an EGFR TKI (eg, erlotinib or gefitinib) within 8 days or approximately 5x half-life, whichever is the longer, of the first dose of study treatment. (If sufficient wash-out time has not occurred due to schedule or PK properties, an alternative appropriate wash-out time based on known duration and time to reversibility of drug related adverse events could be agreed upon by AstraZeneca and the Investigator)
 - Any cytotoxic chemotherapy, investigational agents or anticancer drugs for the treatment of advanced NSCLC from a previous treatment regimen or clinical study within 14 days of the first dose of study treatment.
 - AZD9291 in the present study (ie, dosing with AZD9291 previously initiated in this study)
 - Major surgery (excluding placement of vascular access) within 4 weeks of the first dose of study treatment
 - Radiotherapy with a limited field of radiation for palliation within 1 week of the first dose of study treatment, with the exception of patients receiving radiation to

more than 30% of the bone marrow or with a wide field of radiation which must be completed within 4 weeks of the first dose of study treatment

- Patients currently receiving (or unable to stop use at least 1 week prior to receiving the first dose of AZD9291) medications or herbal supplements known to be potent inhibitors of CYP2C8 and potent inhibitors or inducers of CYP3A4 (Appendix H)
- 2. Any unresolved toxicities from prior therapy greater than Common Terminology Criteria for Adverse Events (CTCAE) grade 1 at the time of starting study treatment with the exception of alopecia and grade 2, prior platinum-therapy related neuropathy
- 3. Spinal cord compression or brain metastases unless asymptomatic, stable and not requiring steroids for at least 4 weeks prior to start of study treatment
- 4. Any evidence of severe or uncontrolled systemic diseases, including uncontrolled hypertension and active bleeding diatheses, which in the investigator's opinion makes it undesirable for the patient to participate in the trial or which would jeopardise compliance with the protocol, or active infection including hepatitis B, hepatitis C and human immunodeficiency virus (HIV). Screening for chronic conditions is not required
- 5. Any of the following cardiac criteria:

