The grading scales found in the current National Cancer Institute CTCAE version 4 will be utilised for all events with an assigned CTCAE grading. For those events without assigned CTCAE grades, the recommendation in the CTCAE criteria that converts mild, moderate and severe events into CTCAE grades should be used. A copy of the current CTCAE version can be downloaded from the Cancer Therapy Evaluation Program website (http://ctep.cancer.gov).

Causality collection

The investigator will assess causal relationship between investigational product and each adverse event, and answer 'yes' or 'no' to the question: 'Do you consider that there is a reasonable possibility that the event may have been caused by the investigational product?'

For SAEs causal relationship will also be assessed for other medication and study procedure. Note that for SAEs that could be associated with any study procedure the causal relationship is implied as 'yes'.

A guide to the interpretation of the causality question is found in Appendix B of this Clinical Study Protocol.

Adverse events based on signs and symptoms

All AEs spontaneously reported by the patient or care provider or reported in response to the open question from the study personnel: 'Have you had any health problems since the previous visit/you were last asked?', or revealed by observation will be collected and recorded in the CRF. When collecting AEs, the recording of diagnoses is preferred (when possible) to recording a list of signs and symptoms. However, if a diagnosis is known and there are other signs or symptoms that are not generally part of the diagnosis, the diagnosis and each sign or symptom will be recorded separately.

Adverse events based on examinations and tests

The results from protocol mandated laboratory tests, vital signs, ECGs and other safety assessments will be summarised in the Clinical Study Report. Deterioration as compared to baseline in these parameters will therefore only be reported as AEs if they fulfil any of the criteria for a SAE, a DLT or are the reason for discontinuation of treatment with the investigational product unless clearly due to progression of disease under study (see Disease progression).

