For the extension cohort, ORR rate is defined as the number (%) of subjects with measurable disease with at least one visit response of CR or PR that is confirmed at least 4 weeks later (according to ICR for the primary analysis). Data obtained up until progression, or last evaluable assessment in the absence of progression, will be included in the assessment of ORR. However, any complete response or partial response which occurred after a further anti-cancer therapy was received will not be included in numerator of the ORR calculation.

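### AE tables include events that start after the next cancer therapy, if within 28 days of stopping AZD9291, and no planned table separates them

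*Protocol*

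**What the plan says.** The safety part of Protocol Section 7.9 has three rules for events after treatment stops.

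- Inside the window: "Any AE occurring within the defined 28 day follow-up period after discontinuation of investigational product will be included in the AE summaries".
- Inside the window but after a switch: "Any adverse events in this period that occur after a patient has received further therapy for cancer" (the text continues: "following discontinuation of investigational product) will be flagged in the data listings").
- Beyond the window: "AEs occurring after the 28 day follow-up period after discontinuation of investigational product will be listed separately, but not included in the summaries".

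The tables that these rules feed are described in the same section: "The number and percentage of patients with adverse events in different categories (eg, causally related, CTCAE grade" 3 or higher, and so on), by dose group and then by system organ class and preferred term. SAEs get their own summary if enough of them occur. A patient whose dose is modified stays in the initial dose group.

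Section 6.4.3 has the investigator answer one yes/no causality question for each event: "Do you consider that there is a reasonable possibility that the event may have been caused by the investigational product". Section 7.1 makes safety and tolerability the primary endpoint for escalation and expansion. Section 7.9 says that safety will be described and not formally tested.

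**The concern.** The plan treats events after a switch as a distinct group, since it takes the trouble to flag them. The flag goes only into listings, and readers of the study report will work mainly from the tables. There, an event that began under the next regimen counts towards the AZD9291 dose group like any other.

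There is no control arm, so the all-cause and grade 3 or higher percentages are the safety result, and no comparator absorbs the extra events. The direction is known: these events can raise the percentages and cannot lower them. The amount can differ between dose groups, because only patients who have stopped AZD9291 and moved on can contribute. A group with more such patients has more opportunity to collect these events, which could blur a comparison of doses.

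The next therapy may also resemble AZD9291. Section 2.1 names single-agent EGFR TKI treatment as one later-line option. Section 3.2 names rash and diarrhoea as toxicities of first-generation EGFR TKIs and expects less of them with AZD9291. An early return to such a drug could add those same events to the AZD9291 tables.

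**Working it through.** The plan states no figure on this point, so there is none to reproduce. The check is a reading of the rules, followed by simple proportions for scale.

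**1. Where an event lands.** Let t be the day of onset after the last dose and s the day on which further anticancer therapy starts.

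| Onset | Summary tables | Listings |
|---|---|---|
| t ≤ 28, t before s or no switch | counted | listed |
| t ≤ 28, t after s | counted | listed with a flag |
| t > 28 | not counted | listed separately |

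The second row is the issue. With assumed days s = 10 and t = 20, the event is counted because 20 ≤ 28, and the start of the new therapy plays no part. Under a cut-off at min(28, s) = 10, the event would leave the second set of tables because 20 > 10. It would stay in the 28-day set.

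**2. Which tables are exposed.** The all-cause, grade 3 or higher and SAE tables have no filter for the source of an event. The causally related tables do, through the causality answer in Section 6.4.3. That filter is not perfect: Appendix B says that ambiguous cases should count as a reasonable possibility, and it lists consistency with drugs of the same class among the factors to weigh. An event attributed only to the next drug nevertheless stays out.

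**3. Which decisions are exposed.** Section 5.1.3 defines a DLT from the first dose to the last day of Cycle 1, and Section 5.1.1 bases escalation on DLTs. The post-treatment summaries do not define that outcome.

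**4. Whether the cut-off can be derived.** Yes. Sections 6.3.8.1 and 6.3.8.2 already collect subsequent cancer therapy, and the listing flag cannot be made without knowing when it started.

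**5. Scale.** The tables count patients, so a patient adds to a cell only if the same category of event had not already occurred on AZD9291. If k patients have their only such event after the switch, the rise in a group of n is 100 × k/n percentage points. Group sizes come from Sections 5.1.1, 5.1.2 and 5.1.2.1.

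| Group | n | k = 1 |
|---|---|---|
| Escalation cohort (maximum) | 6 | 1/6 = 16.7 |
| Expansion cohort | 30 | 1/30 = 3.3 |
| Extension | 175 | 1/175 = 0.6 |

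The value of k is unknown. If k were 0 to 3 in an expansion cohort (an assumption), the rise would be 0 to 3/30, that is 0 to 10 points.

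**The case against.** The case for leaving the rule alone is substantial, and most of it stands.

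- **It is a deliberate, conservative choice.** A fixed 28-day window cannot hide toxicity. This stands for any single all-cause rate. It does not carry over to a comparison between dose groups with different numbers of patients who have switched.
- **Late AZD9291 effects are plausible.** Section 2.2 describes an irreversible inhibitor. Section 2.3 reports radioactivity still present in 42% of tissues measured in pigmented rats at 60 days. This stands, and it is why the 28-day tables should not be replaced.
- **Attribution is available elsewhere.** The causally related tables deal with it, and an all-cause table does not claim to attribute. This stands, with the limits noted for ambiguous and same-class events.
- **An extra table is SAP detail.** The SAP is not at hand and may add one. Section 7.9 does, however, fix how these events are shown and does not require it.

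Two stronger readings are tempting. A reader might infer from the entry washout (cytotoxic chemotherapy, investigational or other anticancer drugs "from a previous treatment regimen or clinical study within 14 days of the first dose of study treatment" are excluded) that patients routinely switch well inside 28 days. Those are minimum intervals for entering this study and say nothing about how soon patients start treatment after AZD9291. The documents show only that the sponsor allows for switching in the window, since the 28-day contact asks about it.

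A reader might also see a double standard in Section 7.7.1, where for the extension "any complete response or partial response which occurred after a further anti-cancer therapy was received will not be included in numerator" of ORR. The two rules are consistent: both lean against the drug. Section 7.7.2 moreover counts PFS events regardless of later therapy, so efficacy has no uniform rule to set against the safety rule.

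**Conclusion.** The point holds as an improvement to presentation, not as an error or contradiction. The all-cause, grade 3 or higher and (if produced) SAE tables by dose group can contain toxicity of the next therapy, and the protocol plans no table that separates it. The causally related tables and the DLT-based escalation decisions are largely unaffected.

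The size cannot be derived. An estimate would need the share of patients who have stopped, the share of those who start new therapy within 28 days, and the rate of new events among them before day 28. The documents give none of these. A reader might multiply assumed values into a count for the 175 extension patients, but the result would only restate the assumptions. It would also overstate the any-grade-3-or-higher table unless patients already counted there were deducted. Section 5.2 selects one dose, 80 mg, for the extension, so that cohort has no planned comparison of starting doses to distort. The per-patient increments above are exact for the stated group sizes. How many patients they apply to is unknown.

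It would also go too far to say that all AE summaries report next-line toxicity as AZD9291 toxicity. The causality tables and the listing flag both stand against that reading.

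**What to change.** Keep the 28-day tables and the listing flag in Section 7.9 as they are. Add one sentence: the all-cause, grade 3 or higher and SAE summaries (the last where produced) will be repeated by dose group, counting adverse events up to 28 days after the last dose of AZD9291 or the start of further anticancer therapy, whichever is first. The difference between the two sets then shows, for each dose group, how much of each percentage depends on events after a switch.

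The cost is one more table set. No new data are needed, since subsequent cancer therapy is already collected. The downside is that delayed AZD9291 toxicity starting after a switch appears only in the 28-day set, so the added tables should be read alongside that set and not in its place.
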